## **13. ADVERSE EVENTS**

#### 13.1. Definitions and Classifications

Adverse Event (AE) – An AE is "any untoward medical occurrence, unintended disease or injury, or untoward clinical signs (including abnormal laboratory findings) in subjects, users or other persons, whether or not related to the investigational medical device.

*Note 1* to entry: This definition includes events related to the investigational medical device or the comparator.

Note 2 to entry: This definition includes events related to the procedures involved.

*Note 3* to entry: For users or other persons, this definition is restricted to events related to investigational medical devices."

An AE includes any condition (including a pre-existing condition) that:

- 1. Was not present prior to the study, but appeared or reappeared following initiation of the study
- 2. Was present prior to the study, but worsened during the study. This would include any condition resulting from concomitant illnesses, reactions to concomitant medications, or progression of disease states
- 3. Pregnancy must be documented as an adverse event and must be reported to the clinical monitor and to the Sponsor immediately upon learning of the event

Serious Adverse Event (SAE) – An SAE is any untoward medical occurrence that:

- Results in death
- Is life threatening
- Requires in-patient hospitalization or prolongation of existing hospitalization
- Results in persistent or significant disability/incapacity (e.g., a sight threatening event, a significant persistent or permanent change, impairment, damage, or disruption to the subject's body)
- Is a congenital anomaly/birth defect
- Requires intervention to prevent permanent damage (the use of the test article resulting in a condition which requires medical or surgical intervention to preclude permanent impairment of the body structure or a body function). Important medical events that may not result in death, be life-threatening, or require hospitalization may be considered an SAE when, based upon appropriate medical judgment, they may jeopardize the patient or subject and may require medical or surgical intervention to prevent one of the outcomes listed in the above definition

Diagnoses and conditions that are considered Ocular Serious Adverse Events include, but not limited to:

- Microbial Keratitis (MK)
- Iritis (including cells in the anterior chamber)
- Permanent decrease in best spectacle corrected visual acuity equivalent to 2 acuity lines or greater
- Central Corneal Opacity
- Central Corneal Neovascularization

- Uveitis
- Endophthalmitis
- Hypopyon
- Hyphemia
- Penetration of Bowman's Membrane
- Persistent Epithelial Defect
- Limbal cell Damage leading to Conjunctivalization

**Significant Adverse Events** – Those events that are usually symptomatic and warrant discontinuation (temporary or permanent) of the test article (excluding Serious Adverse Events).

Diagnoses and conditions that are considered Ocular Significant Adverse Events include, but not limited to the following:

- Contact Lens Induced Peripheral Ulcer (CLPU)
- Significant Infiltrative Events (SIE)
- Superior Epithelial Arcuate Lesions (SEALs)
- Any Temporary Loss of > 2 Lines of BSCVA
- Other grade 3 or higher corneal findings, such as abrasions or edema
- Non-contact lens related corneal events e.g. Epidemic Keratoconjunctivitis (EKC)
- Asymptomatic Corneal Scar
- Any corneal event which necessitates temporary lens discontinuation > 2 weeks

**Non-Significant Adverse Events** – Those conditions that are usually asymptomatic and usually do not warrant discontinuation (temporary or permanent) of the test article. However, the Investigator may choose to treat as a precautionary measure.

Diagnoses and conditions that are considered Ocular Non-Significant Adverse Events include, but not limited to the following:

- Non-significant Infiltrative Event (NSIE)
- Contact Lens Papillary Conjunctivitis (CLPC)
- Superficial Punctate Keratitis (SPK)
- Conjunctivitis: Bacterial, Viral, Allergic
- Blepharitis
- Meibomianitis
- Contact Dermatitis
- Localized Allergic Reactions
- Any corneal event not explicitly defined as serious or significant adverse event, which necessitates temporary lens discontinuation < 2 weeks

Adverse Device Effect (ADE) – An ADE is an "adverse event related to the use of an investigational medical device.

*Note 1* to entry: This definition includes adverse events resulting from insufficient or inadequate instructions for use, deployment, implantation, installation, or operation, or any malfunction of the investigational medical device.

*Note 2* to entry: This definition includes any event resulting from use error or from intentional misuse of the investigational medical device."

**Unanticipated Adverse Device Effect (UADE)** – Any serious adverse effect on health or safety or any life-threatening problem or death caused by, or associated with, the test article, if that effect, problem, or death was not previously identified in nature, severity, or degree of incidence in the investigational plan, Investigator's Brochure or protocol, or any other unanticipated serious problem associated with the test article that relates to the rights, safety and welfare of subjects.

# 13.2. Assessing Adverse Events

In conjunction with the medical monitor, the Investigator will evaluate adverse events to ensure the events are categorized correctly. Elements of categorization will include:

- Seriousness/Classifications (see definition in Section 13.1)
- Causality or Relatedness i.e. the relationship between the test article, study treatment or study procedures and the adverse event (not related; unlikely related; possibly related; related see definition in Section 13.2.1)
- Adverse Event Severity Adverse event severity is used to assess the degree of intensity of the adverse event (mild; moderate; severe for all events see definition in Section 0)
- Outcome not recovered or not resolved; recovering or resolving; recovered or resolved with sequelae; recovered or resolved; death related to adverse event; unknown
- Actions Taken none; temporarily discontinued; permanently discontinued; other

## 13.2.1. Causality Assessment

**Causality Assessment** – A determination of the relationship between an adverse event and the test article. The test article relationship for each adverse event should be determined by the investigator using these explanations:

- Not Related- An adverse event that is not related to the use of the test article, study treatment or study procedures
- Unlikely Related An adverse event for which an alternative explanation is more likely, e.g. concomitant treatment, concomitant disease(s), or the relationship of time suggests that a causal relationship is not likely
- Possibly Related An adverse event that might be due to the use of the test article, or to the study treatment or study procedures. An alternative explanation, e.g. concomitant treatment, concomitant disease(s), is inconclusive. The relationship in time is reasonable. Therefore, the causal relationship cannot be excluded
- Related An adverse event that is listed as a possible adverse effect (device) or adverse reaction (drug) and cannot be reasonably explained by an alternative explanation, e.g. concomitant treatment of concomitant disease(s). The relationship in time is very suggestive, e.g. it is confirmed by de-challenge and re-challenge

## 13.2.2. Severity Assessment

**Severity Assessment** – A qualitative assessment of the degree of intensity of an adverse event as determined by the Investigator or reported to him/her by the subject. The assessment of

severity is made irrespective of test article, study treatment or study procedure relationship or seriousness of the event and should be evaluated according to the following scale:

- Mild Event is noticeable to the subject, but is easily tolerated and does not interfere with the subject's daily activities
- Moderate Event is bothersome, possible requiring additional therapy, and may interfere with the subject's daily activities
- Severe Event is intolerable, necessitates additional therapy or alteration of therapy and interferes with the subject's daily activities

# **13.3. Documentation and Follow-Up of Adverse Events**

The recording and documenting of adverse events (ocular and non-ocular) begins when the subjects are exposed to the test article, study treatment or study procedure. Adverse events reported before the use of test article, start of study treatment, or study procedures will be recorded as medical history. However, if the condition deteriorates at any time during the study it will be recorded and reported as an AE. Untoward medical events reported after the subject's exit from the study will be recorded as adverse events at the discretion of the Investigator.

Upon finding an adverse event, the Principal Investigator will document the condition in the subject record and in the eCRFs. He/she will complete the Adverse Event /eCRF.

Complete descriptions of all adverse events must be available in the subject record. All Adverse Events including local and systemic reactions not meeting the criteria for "serious adverse events" shall be captured on the appropriate case report form or electronic data system. All adverse events occurring while the subject is enrolled in the study must be documented appropriately regardless of relationship.

It is the Investigator's responsibility to maintain documentation of each reported adverse event. All adverse events will be followed in accordance with applicable licensing requirements. Such documentation will include the following:

- Adverse event (diagnosis not symptom)
- Drawings or photographs (where appropriate) that detail the finding (e.g., size, location, and depth, etc.)
- Date the clinical site was notified
- Date and time of onset
- Date and time of resolution
- Adverse event classification, severity, and relationship to test articles, as applicable
- Treatment regimen instituted, including concomitant medications prescribed, in accordance with applicable licensing requirements
- Any referral to another health care provider if needed
- Outcome, ocular damage (if any)
- Likely etiology
- Best corrected visual acuity at the discovery of the event and upon conclusion of the event

In addition, if an infiltrate(s) is present, he/she will complete the Corneal Infiltrate Assessment eCRF. Where necessary, a culture of the corneal lesion will be collected to determine if the infection is microbial in nature. If cultures are collected, the date of culture collection and laboratory utilized will be recorded.

Changes in the severity of an AE shall be documented to allow an assessment of the duration of the event at each level of intensity to be performed. Adverse events characterized as intermittent require documentation of the onset and duration of each episode. Changes in the assessment of relationship to the Test Article shall also be clearly documented.

Subjects who present with an adverse event shall be followed by the Investigator, within licensure, until all signs and symptoms have returned to pre-treatment status, stabilized, or been satisfactorily resolved. If further treatment beyond licensure is required, the patient will be referred to the appropriate health care provider. The Investigator will use his/her clinical judgment as to whether a subject reporting with an adverse event will continue in the study. If a subject is discontinued from the study, it will be the responsibility of the Investigator to record the reason for discontinuation. The Investigator will also document the adverse event appropriately and complete the Adverse Event eCRF. Any subjects with ongoing adverse events related to the test article, study treatment or study procedures, as of the final study visit date, should be followed to resolution of the adverse event or until referral to an appropriate health care provider, as recommended by the Investigator. Non-ocular adverse events that are not related to the test article, study treatment, or study procedures may be recorded as "ongoing" without further follow-up.

## **13.4. Reporting Adverse Events**

The Investigator will notify the Sponsor of an adverse event by e-mail, facsimile, or telephone as soon as possible and no later than 24 hours from discovery for any serious /significant adverse events, and 2 days from discovery for any non-significant adverse event. In addition, a written report will be submitted by the Principal Investigator to the IEC/IRB according to their requirements (Section 13.4.2). The report will comment whether the adverse event was considered to be related to the test article, study treatment or study procedures.

## 13.4.1. Reporting Adverse Events to Sponsor

## Serious/Significant Adverse Events

The Investigator will inform the sponsor of all serious/significant adverse events occurring during the study period as soon as possible by e-mail, fax, or telephone, but no later than 24 hours following discovery of the event. The Investigator is obligated to pursue and obtain information requested by the Sponsor in addition to that information reported on the eCRF. All subjects experiencing a serious/significant adverse event must be followed up and all outcomes must be reported.

When medically necessary, the Investigator may break the randomization code to determine the identity of the treatment that the subject received. The Sponsor and study monitor should be notified prior to unmasking the test articles.

In the event of a serious/significant adverse event, the Investigator must:

- Notify the Sponsor immediately
- Obtain and maintain in the subject's records all pertinent medical information and medical judgment for colleagues who assisted in the treatment and follow-up of the subject
- Provide the Sponsor with a complete case history which includes a statement as to whether the event was or was not related to the use of the test article
- Notify the IEC/IRB as required by the IEC/IRB reporting procedure according to national regulations

## Unanticipated (Serious) Adverse Device Effect (UADE)

In the event of an Unanticipated (Serious) Adverse Device Effect (UADE), the Investigator will submit a report of the UADE to the Sponsor and IEC/IRB as soon as possible, but no later than 24 hours after the Investigator first learns of the effect. This report is in addition to the immediate notification mentioned above.

The Sponsor must conduct an evaluation of the UADE and must report the results of the evaluation to FDA, the IEC/IRB and participating Investigators within 10 working days after the Sponsor first receives notification of the effect.

## Non-Serious Adverse Events

All non-serious adverse events, including non-serious adverse device effects, will be reported to the sponsor by the Investigator no later than 2 days from discovery.

#### 13.4.2. Reporting Adverse Events to the Responsible IEC/IRB and Health Authorities

Adverse events that meet the IEC/IRB requirements for reporting must be reported within the IEC/IRB's written guidelines. Each clinical site will refer to and follow any guidelines set forth by their Approving IEC/IRB. Each clinical site will refer to and follow any guidelines set forth by their local governing Health Authorities.

The Sponsor will report applicable Adverse Events to the local health authorities according the written guidelines, including reporting timelines.

#### 13.5. Event of Special Interest

None

## **13.6.** Reporting of Pregnancy

Subjects reporting pregnancy (by self-report) during the study will be discontinued after the event is recorded as an Adverse Event. Once discontinued, pregnant participants and their fetuses will not be monitored for study related purposes. At the Investigator's discretion, the study participant may be followed by the Investigator through delivery. However, this data will not be collected as part of the clinical study database. Pregnant participants are not discontinued from contact lens or solution related studies for safety concerns, but due to general concerns relating to pregnancy and contact lens use. Specifically, pregnant women are discontinued due to fluctuations in refractive error and/or visual acuity that occur secondary to systemic hormonal changes, and not due to unforeseen health risks to the mother or fetus.

# **14. STATISTICAL METHODS**

#### 14.1. General Considerations

Statistical Analysis will be undertaken by the sponsor or under the authority of the sponsor. A general description of the statistical methods to be implemented in this clinical trial is outlined below.

All data summaries and statistical analyses will be performed using the SAS software Version 9.4 (SAS Institute, Cary, NC). Throughout the analysis of data, the results for each subject/eye will be used when available for summarization and statistical analysis. Unscheduled visits will be summarized separately and will be excluded from the statistical analysis.

Summary tables (descriptive statistics and/or frequency tables) will be provided for all baseline variables, efficacy variables and safety variables as appropriate. Continuous variables will be summarized with descriptive statistics (n, mean, standard deviation (SD), median, minimum and maximum). Frequency count and percentage of subjects or eyes within each category will be provided for categorical data.

## 14.2. Sample Size Justification

The plan is to enroll a maximum of 66 subjects with a minimum target of 60 subjects to complete. The sample size was chosen by the study responsible clinician and was not based on any empirical power calculation. Furthermore, a power calculation cannot be provided for any of the primary endpoints because no historical data is available. This data from this study will be utilized in the sample size calculations for any additional follow-up studies.

#### 14.3. Analysis Populations

#### **Safety Population:**

All subjects who were administered any test article excluding subjects who drop out prior to administering any test article. At least one observation should be recorded.

#### **Per-Protocol Population:**

All subjects who have successfully completed all visits and did not substantially deviate from the protocol as determined by the trial cohort review committee prior to database hard lock (Per-Protocol Population). Justification of excluding subjects with protocol deviations in the per-protocol population set will be documented in a memo to file.

## Intent-to-Treat (ITT) Population:

All randomized subjects regardless of actual treatment and subsequent withdrawal from study or deviation from protocol. At least one observation should be recorded.

## 14.4. Level of Statistical Significance

Each primary and secondary hypothesis will be tested individually using a type I error rate of 5%.

# 14.5. Primary Analysis

# Light Scattering (Two-point Light Spread Function)

This is defined as the minimum distance (mm) that two points of light are completely distinct. This threshold will be analyzed by a linear mixed model. Sequence of lens wear, lens type, age group, dominant eye and the interaction between lens type and age group will be included in the model as fixed effects. An appropriate covariance structure will be used to model the residual errors between measurements between eyes within a subject. The variance-covariance structure will be selected based on the finite-sample corrected Akaike's Information Criterion Corrected (AICC). The structure that returns the lowest AICC will be deemed the most appropriate structure. Covariance structures under consideration include:

- Unstructured (UN)
- Compound Symmetry (CS)
- Heterogeneous Compound Symmetry (CSH)

Heterogeneous covariance structures across lens type may be considered if necessary. The Kenward and Roger method (Kenward and Roger, 1997) will be used for the denominator degrees of freedom.

Comparisons between lenses (Test inactivated vs Control and Test activated vs Control) will be carried out using 2-sided 95% confidence intervals constructed for the least-square mean (LSM) difference (Test – Control). Statistically significantly lower differences of the Test lens relative to the Control lens will be concluded if the upper limit of the 95% confidence interval is below 0. If the interaction between lens type and age is significant then comparisons between lenses will be made within age group.

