#### 2.3. Hypotheses

Primary Hypotheses (each is considered independent)

- 1. Light Scattering
  - a. The Test lens (in the absence of an additional UV/HEV light source) will be statistically lower than the Control lens with respect to light scattering as measured using the two-point light threshold instrument.
  - b. The Test lens (in the presence of an additional UV/HEV light source) will be statistically lower than the Control lens with respect to light scattering as measured using the two-point light threshold instrument.

- 2. Haloes
  - a. The Test lens (in the absence of an additional UV/HEV light source) will be statistically lower than the Control lens with respect to halos. This is measured using the halometer instrument.
  - b. The Test lens (in the presence of an additional UV/HEV light source) will be statistically lower than the Control lens with respect to halos. This is measured using the halometer instrument.
- 3. Starbursts
  - a. The Test lens (in the absence of an additional UV/HEV light source) will be statistically lower than the Control lens with respect starbursts as measured using the halometer instrument.
  - b. The Test lens (in the presence of an additional UV/HEV light source) will be statistically lower than the Control lens with respect starbursts as measured using the halometer instrument.

Secondary Hypotheses (each is considered independent)

- 1. The Test lens (in the absence of an additional UV/HEV light source) will be statistically lower than the Control lens with respect to photostress recovery time (seconds) as measured using the optical bench instrument.
- 2. The Test lens (in the absence of an additional UV/HEV light source) will be statistically higher than the Control lens with respect to disability glare threshold as measured using the optical bench instrument.
- 3. The Test lens (in the absence of an additional UV/HEV light source) will be statistically lower than the Control lens with respect to discomfort glare (eyelid squinting) as measured using the optical bench instrument.
- 4. The Test lens (in the absence of an additional UV/HEV light source) will be statistically higher than the Control lens with respect to chromatic contrast threshold than as measured using the optical bench instrument.

Other Hypotheses

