## Starburst

Starbursts will be quantified by the diameter of the light's lateral spread. A calibrated custommade micrometer (two sides with reverse threading) will be used to spread two posts out from a central mid-point). Those posts can then be used to define the outer boundaries of the starburst image (i.e. the diameter). The diameter of the light's lateral spread will be analyzed and tested in the same manner as described for light scattering above.

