## Halos

Halos will be quantified by the diameter (mm) of outer edges of the halo image and is measured using the same micrometer as for starbursts and light scattering. The diameter will be analyzed using the same model as described for light scattering.

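### Section 14.5 compares both Test activation states with one Control whose lamp state is not stated, so on some readings of the model a lamp effect on the Control eye enters the primary contrasts

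*Combined protocol and SAP*

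**What the plan says.** Section 14.5 sets two contrasts for light scattering: "Comparisons between lenses (Test inactivated vs Control and Test activated vs Control) will be carried out using 2-sided 95% confidence intervals". The fixed effects are given as follows: "Sequence of lens wear, lens type, age group, dominant eye and the interaction between lens type and age group will be included". None of them is lamp state, testing round or activation order. The covariance is for "residual errors between measurements between eyes within a subject", and "The structure that returns the lowest AICC will be deemed the most appropriate structure". There is also an age rule: "If the interaction between lens type and age is significant then comparisons between lenses will be made within age group". Starbursts "will be analyzed and tested in the same manner as described for light scattering above", and for halos "The diameter will be analyzed using the same model as described for light scattering". The wording therefore governs all six primary hypotheses.

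Section 2.3 attaches the lamp to the Test lens only. For halos, the Test lens in the absence (a) or presence (b) "of an additional UV/HEV light source) will be statistically lower than the Control lens with respect to halos". Control carries no lamp qualifier.

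On what is measured at Visit 2, the documents differ:

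- Section 7.2, Psychometric Testing B, steps 1 to 4: all three tests are done once with the activating lamp and once without, values are recorded for OD and OS, and the LEDs stay lit while readings are taken.
- Section 1 (end of Practical implications), section 2.2 (conditions A, B, C) and the Testing B apparatus paragraph: three conditions, of which one is Control and two are Test.
- Section 5.1: the randomised order is described as the order of Test lens activation.

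**The concern.** The design is contralateral, so in each lamp round one eye wears Test and the other wears Control. Read literally, section 7.2 gives four readings per endpoint: Test-off, Test-on, Control-off and Control-on. Section 14.5 does not say which Control reading, or what combination of the two, each Test state is compared with.

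This matters because the lamp is in the optical path during the measurement. If lamp light changes the halo, starburst or two-point threshold in the Control eye, an unmatched contrast mixes a lens effect with a lamp effect. That could produce an apparent benefit in one activation state and mask a real one in the other. Randomising the activation order does not protect against this, because the lamp effect belongs to the condition and not to the order. Choosing the covariance by AICC does not supply a missing lamp term in the mean model either.

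**Working it through.** The plan has no figure to reproduce. Section 14.2 says the sample size was not based on a power calculation and that no historical data exist, so no SD, effect size or correlation is given.

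**Step 1: bias by reading of Control.** Let L = Control-on minus Control-off, and let the Control mean put weight w on the lamp-on reading. Then:

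- inactivated contrast = (Test-off − Control-off) − wL
- activated contrast = (Test-on − Control-on) + (1 − w)L

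| Reading of Control | Bias, inactivated | Bias, activated |
|---|---|---|
| Same lamp round (fit per lamp state) | 0 | 0 |
| Both readings pooled, w = 1/2 | −L/2 | +L/2 |
| Lamp-off only, w = 0 | 0 | +L |
| Lamp-on only, w = 1 | −L | 0 |

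The lamp effect on the Test eye does not appear, so no common effect on both eyes need be assumed.

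**Step 2: a three-level lens type fitted by generalised least squares.** Take unit variances, same-eye correlation r_s, between-eye correlation r_w within a round and r_a across rounds. Let ρ = (r_w − r_a)/(1 − r_s).

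- Share of L in each contrast = (1 − ρ)/2
- Contrast variance = (1 + r_s − r_w − r_a) + (1 − r_s)(1 − ρ²)/2

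With r_s = 0.8, r_w = r_a = 0.5: ρ = 0, share 0.50, variance 0.8 + 0.1 = 0.9, SD 0.949.

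With r_s = 0.8, r_w = 0.6, r_a = 0.5: ρ = 0.5, share 0.25, variance 0.7 + 0.075 = 0.775, SD 0.880.

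The matched contrast has SD √(2 − 2r_w): 1.000 and 0.894 respectively.

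**Step 3: illustrative false-benefit rates.** Inputs: n = 60 (section 14.2), a benefit claimed when the upper 95% limit is below 0 (section 14.5), no lens effect, and the assumed correlations above. The rate is the probability that a noncentral t with 59 df falls below −2.001, with noncentrality −(share × L × √60)/SD. Example: L = 0.2 pooled gives 0.1 × 7.746/0.949 = 0.816, so 12.4%.

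| Absolute L (SD) | Pooled Control, 0.8/0.5/0.5 | Lamp-off Control only (SD 1.000) |
|---|---|---|
| 0 | 2.5% | 2.5% |
| 0.02 | 3.0% | 3.5% |
| 0.05 | 3.9% | 5.7% |
| 0.1 | 6.0% | 11.5% |
| 0.2 | 12.4% | 33.1% |

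In the pooled column the affected contrast is the inactivated one if the lamp enlarges the image and the activated one if it shrinks it. The last column is for the activated contrast when the lamp shrinks the image. With same-round correlation 0.6, the pooled rate at L = 0.2 is 6.3% (0.05 × 7.746/0.880 = 0.440). Same-round matching gives 2.5% throughout.

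**Step 4: price of matching when L = 0.** Power for a 0.36 SD benefit, with noncentrality 0.36 × 7.746/SD:

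- No same-round coupling: 78% matched (SD 1.000) against 82% pooled (SD 0.949).
- Same-round correlation 0.6: about 87% (SD 0.894) against 88% (SD 0.880).

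**Step 5: what the documents say about the size of L.** Section 7.2 gives 0.07 mW/cm² for the lamp and 11 mW/cm² for mid-day sun: 0.07/11 = 0.6%. The Control package insert (Appendix C) gives transmittance under 10% for 316 to 380 nm. The lamp band is 365 to 400 nm, so 380 to 400 nm is outside that figure. Nothing gives L itself.

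**The case against.** The strongest reply is that section 14.5 can be read without any bias. Its covariance wording describes two eyes within a subject, a two-record structure, and section 14.6 uses the same wording for Visit 1, where there is only one lamp state. Lens type can mean the two lenses of Table 1. Fitted once per lamp state, the model yields Test-off minus Control-off and Test-on minus Control-on. That agrees with the both-eyes procedure in section 7.2, the objective in section 2.1 and the within-subject rationale in section 4.2. This stands: a reader might infer that the primary model is mis-specified, and the documents do not establish that. They leave several readings open. Against it, section 14.5 names both contrasts together with a single Control, and three other places list three conditions, so matching is not what the text says.

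Second, L may be close to zero, given the weak lamp and the Control lens's own UV absorption. This also stands, and at L = 0.02 SD the pooled rate is only 3.0%. But the documents do not show that L is zero.

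Third, the larger rates assume that eyes correlate no more within a round than across rounds. Rounds are separate blocks at least 10 minutes apart, so some coupling is plausible, and it roughly halves the 12.4% figure.

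Finally, the Figure 1 flowchart and the apparatus figures could not be read in the copy reviewed. If they show a Control lamp state, that part is answered, but the conflict between the text sections would remain.

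**Conclusion.** The documentary conflict is certain: section 7.2 implies Control readings in both lamp states, other sections list one Control, and the analysis of all six primary hypotheses does not say which is used. The bias is conditional. It is zero if the model is fitted per lamp state, plus or minus half of L (less with same-round coupling) if a three-level lens type is fitted to all readings, and all of L in the activated contrast if Control is lamp-off only.

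A reader might go on to infer that the trial's false-benefit rate will be 12% or more. The documents do not support that. L, the SDs and the correlations are all assumed here, and L may be small. The rates show only how an unmatched contrast would behave. The point merits correction because the ambiguity covers every primary contrast and matching removes the risk at little cost.

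**What to change.** 1. Reconcile section 1, section 2.2, section 2.3 and the Testing B apparatus paragraph with the Testing B steps in section 7.2, and state whether the Control eye is read in both lamp states.
2. In section 14.5, for all three endpoints, define hypotheses a as Test-off minus Control-off and hypotheses b as Test-on minus Control-on, using the Control eye from the same lamp round.
3. Choose one implementation in advance. Either fit the existing model once per lamp state, applying its age-interaction rule within each fit, or fit a lens-by-lamp model with a covariance over both eyes and both rounds. In either case include the randomised activation order.
4. If Control is in fact read in one lamp state only, reword the unmatched hypothesis as lens plus lamp against Control without a matched lamp.

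If both Control readings are taken, the cost is wording and model code, plus the small loss of precision at L = 0 shown in the working. If only one is taken, the cost is a weaker claim for the unmatched hypothesis.
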